1. PURPOSE OF THE STUDY

a. Brief Summary

American Indians and Alaska Natives (AIAN) have disproportionate rates of obesity and diabetes and are more likely to suffer from psychosocial stressors than their white counterparts. These stressors increase obesity risks and are barriers to fully participating in lifestyle interventions. While lifestyle interventions such as the Diabetes Prevention Program have been effective among racial/ethnic groups, including American Indians, these interventions have not been studied in primary care or community-based settings and have not addressed barriers pertaining to psychosocial stressors or historical traumas.

b. Objectives

Our specific aims are:

1. To deepen engagement of patient and provider stakeholders to better understand the patient-centered perspective on psychosocial issues that influence progression to diabetes among urban AIANs.
2. To refine, strengthen, and test an enhanced DPP that incorporates psychosocial support for urban AIANs in a RCT (n=204).
3. To rapidly disseminate research findings to key stakeholders at the local state, and national level. These aims address the priority of eliminating health disparities by addressing the context of prevalent diabetes in a marginalized population.

c. Rationale for Research in Humans

Human subjects must be used to inform the development of a culturally appropriate and enhanced diabetes prevention program addressing psychosocial stressors and to evaluate the effectiveness of this program compared to the standard program.

2. STUDY PROCEDURES

a. Procedures

Phase 1, we will use the first six months of the study to refine and strengthen the intervention and study protocol by analyzing existing deidentified data from the Indian Health Center and using Talking Circles(TCs), Modified Photo Voice, and Digital Storytelling:

- 1) We will analyze existing, deidentified pre- and post-intervention data from the existing IHC diabetes prevention program to identify information on the association between mental health, BMI, and other indicators.
- 2) Talking Circles: A total of five Talking Circles (TCs) will be conducted with participants (50 total participants) who are interested in urban AIAN health and wellness to gain relevant insights. Each talking circle will have up to 10 participants in the session and, in keeping with tradition, each session will have unlimited time. Skilled facilitators will lead participants in a process to set ground rules, share a meal, and participate in guided discussions. Participants will decide if the session will be audio recorded or if an alternative method to summarize the key points from the session will be used.
- 3) Modified Photo Voice: Ten AIAN community members who participated in a TC will be invited to participate in a 6-week Modified Photo Voice project. Participants will participate in 6 sessions (one session per week) use a digital camera to take photographs and write photo narratives pertaining to health needs and assets in AIAN communities. During photo sharing sessions, participant discussions will be audio recorded and transcribed for data analysis to uncover relevant themes. Participants will share photos and findings with stakeholders during a Community Action Board (CAB) meeting so that the CAB can use these findings to develop appropriate interventions for the enhanced diabetes prevention program.
- 4) Digital Storytelling: Ten AIAN community members who participated in a TC but did not participate in the Modified Photovoice project, will be invited to participate in a 3-day digital storytelling project. A skilled facilitator will guide participants through a process of storytelling combined with technology and digital media to create a 1-3 minute video. Open-ended interviews will be conducted with participants one week after video completion. These interviews will be audio recorded and transcribed to identify relevant themes. Participants will be invited to present their videos to the Community Action Board and discuss their experience with the process.

In phase 2, we will conduct a randomized controlled trial with up to 210 participants for the 16 week intervention.

Recruited participants will be screened using a set of entry criteria, including a BMI between 30 and 55, and one criterion for metabolic syndrome (e.g. triglycerides, HDL, blood pressure, fasting blood glucose). Patients cannot already have received a diagnosis of Type II diabetes (among other exclusionary criteria). Potentially eligible patients complete a written consent process which includes a thorough presentation of the study's purpose, procedures, and potential risks & benefits.

- 1) Participants will be referred or self-referred to the study.
- 2) Initial Screen (self-report): Conducted either in-person or by phone.
- 3) Clinical Screen*: In-person verification of eligibility measurements (ie. Weight and lab measurements). *The clinical screen can be skipped if clinical values <3 months are available (ie. weight and lab measurements)
- 4) Consent: Written, informed consent will be obtained

Participants will be recruited by Timpany Center staff and community members. If they are otherwise eligible except that some of their information is more than 3 months old, we will conduct a clinical screening to collect recent blood pressure, and blood test for cholesterol and blood sugar. They will consent in- person for the clinical screening. Eligible participants will receive an explanation about the study and sign the full study consent form. After signing the consent form, the participant completes baseline data collection. This includes an interviewer administered questionnaire, a blood test, clinical measurements, and wearing a pedometer for 7 days. After all baseline data is collected, the participant is randomly assigned to ONE of two groups: 1) diabetes prevention program (DPP) or 2) enhanced diabetes prevention program (DPP+).

There are 102 people in the standard DPP and 102 people in the enhanced diabetes prevention program to address historical trauma (DPP+). Participants will complete 3 evaluations during the research study: baseline, 5 months (1 week following the conclusion of intervention). Participants enrolled in the last cohorts will not have as many follow-up evaluations as those enrolled in initial cohorts. The evaluations include blood draws, other measurements (blood pressure, height, weight, and waist circumference), and a series of questionnaires. Blood samples and other measurements will be collected at all of the evaluation visits (baseline, 5 months, 8 months, 14 months, and 20 months) after a more than 8 hour fast. The volume of most blood samples will be 20 cc's (approximately 1.5 tablespoons). Any samples left over after analysis will be destroyed when the study is completed. Questionnaires include a series of questions about their eating patterns, physical activity habits, smoking status, past medical history, current medications, use of additional health care resources, resilience, and emotional status. Questionnaires will be filled out at the clinic visits at baseline, 5 months, 8 months, 14 months, and 20 months.

b. Procedure Risks

We have designed this study to be least risky through the following means:

- 1) The intervention targets improvement of behaviors (diet, exercise, stress reduction) that can help decrease weight; thereby, decreasing the chance of cardiovascular disease.
- 2) The intervention recommendations are based on accepted clinical guidelines.
- 3) The intervention builds on previous trials conducted by key investigators on this project.

c. Use of Deception in the Study:

Deception will not be used in the research study.

d. Use of Audio and Video Recordings

We may use audio recording or video recording for Talking Circles, Modified Photovoice, Digital Storytelling, CAB meetings, and intervention classes for research purposes to analyze transcribed data and for educational purposes in order to review how the health educators are presenting the protocol to the participants. We may also use audio recording for interviewing participants about how they feel about the health education they receive.

We will also use camera pictures (and accompanying written or audio narrative) and video footage created by participants to share cultural stories, and perceptions of health needs and assets in the AIAN community. Audio recordings from interview debriefings will be destroyed once they have been transcribed. Photos, videos, and accompanying audio from Modified Photo Voice and Digital Storytelling maybe used for educational purposes, such as during community presentations or scientific meetings and

conferences. Photos, videos, and audio will not be linked to individuals unless we have received express written approval to use the media for a given purpose.

e. Alternative Procedures or Courses of Treatment

Standard treatments for weight management and diabetes prevention will be described to all participants. This program utilizes existing standards of care. No standard treatment is being withheld. The alternative is not to participate and to individually pursue an exercise program(s), work with a personal trainer, or consult with a dietitian on diet modifications.

f. Will it be possible to continue the more (most) appropriate therapy for the participant(s) after the conclusion of the study?

If funding allows, we will continue with the enhanced diabetes prevention program. However, the enhanced components of the program may not typically be covered by the Indian Health Center of Santa Clara Valley, so we do not guarantee it.

g. Study Endpoint(s)

Because our primary end point is increased resilience and weight loss for diabetes prevention, we do not expect any adverse events to cause us to terminate the study early. We plan to continue the study for the full 20 months and provide participants with the opportunity to participate in several follow-up focus groups to contextualize study results.

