- iv. Inappropriate for moderate exercise according to the Revised Physical Activity Readiness Questionnaire;
- v. Pregnant, planning to become pregnant, or lactating;
- vi. Family household member already enrolled in the study;
- vii. Already enrolled or planning to enroll in a clinical trial that would limit full participation in the

study;

- viii. Resident of a long- term care facility;
- ix. Lack of spoken English by patient or a household member > 18 y who can serve as interpreter;
- x. Plans to move during the study period (9 months post-randomization);
- xi. Investigator discretion for clinical safety or adherence reasons (e.g., unstable housing, chronic pain).

i. Screening Procedures

Exclusion criteria for Randomized Controlled Trial

- i. Significant medical comorbidities, including uncontrolled metabolic disorders (e.g., thyroid, diabetes, renal, liver), unstable heart disease, heart failure, and ongoing substance abuse;
- ii. On greater than 10 prescription medications;
- iii. Psychiatric disorders requiring atypical antipsychotics or multiple medications;
- iv. Inappropriate for moderate exercise according to the Revised Physical Activity Readiness Questionnaire;
- v. Pregnant, planning to become pregnant, or lactating;
- vi. Family household member already enrolled in the study;
- vii. Already enrolled or planning to enroll in a clinical trial that would limit full participation in the study;
- viii. Resident of a long-term care facility;
- ix. Lack of spoken English by patient or a household member > 18 y who can serve as interpreter;
- x. Plans to move during the study period (9 months post-randomization);
- xi. Investigator discretion for clinical safety or adherence reasons (e.g., unstable housing, chronic pain).

j. Participation in Multiple Protocols

Participants will be asked about participation in other studies during the screening process. If they are in another study, they will need to gain approval from both study protocol directors to remain in both studies. Additionally, they will be asked to inform study researchers if they join another study during the duration of their participation in this study.

k. Payments to Participants

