A Patient-Centered Strategy for Improving Diabetes Prevention in Urban American Indians

02266576

Statistical Analysis Plan

October 9, 2019

CHANGES FROM ORIGINAL PROTOCOL

1. The second investigational site was changed from Indian Health Center of Santa Clara Valley to the Timpany Center at the San Jose State University Research Foundation.
2. Blood samples were obtained by fingerstick method rather blood draw.

METHODS

The primary model for participant j at time k nested in cohort i

$$\begin{aligned} \text{Outcome}_{ijk} = & \beta_0 + \beta_{0i} \\ & + \beta_{0ij} + \beta_1 \text{Intervention}_j + \beta_2 \text{Month6}_{jk} + \beta_3 \text{Month12}_{jk} + \beta_4 \text{Month18}_{jk} \\ & + \beta_5 \text{Intervention}_j * \text{Month6}_{jk} + \beta_6 \text{Intervention}_j \\ & * \text{Month12}_{jk} + \beta_7 \text{Intervention}_j * \text{Month18}_{jk} + \beta_8 \text{Gender}_j + \varepsilon_{ijk} \end{aligned}$$

will be used to test the co-primary hypotheses that BMI will decrease and quality of life will increase in the enhanced DPP arm relative to the standard DPP arm upon completion of the study. The linear regression model includes a random intercept β_{0i} to account for within cohort correlation, a random intercept β_{0ij} to account for within participant correlation, and adjusts for gender (Gender_j), the stratification factor for randomization. Intervention_j indicates that participant j is in the enhanced DPP arm and Month6_{jk} , Month12_{jk} , and Month18_{jk} indicate whether observation k from subject j is at month 6, 12, or 18, respectively. To test whether the change in the primary outcome from baseline at 12 months differs between the standard and enhanced arms, we will test the null hypothesis that $\beta_6 = 0$ using the Wald test. Each outcome will be tested at a two-sided $\alpha = 0.05$ for an overall $\alpha = 0.10$.

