Our study was designed to provide sufficient statistical power to test the study's co-primary hypothesis that the enhanced DPP will result in greater weight loss and quality of life improvement compared to the standard DPP. In determining the sample size we considered the definition of clinically significant weight loss, the standard deviation of weight change in past clinical trials of lifestyle interventions, and acceptable levels of Type I and Type II errors. Our power estimates are based on simplified assumptions and the actual power may be different because of the correlated errors induced by the cohort effect and the repeated measures over time. In the original DPP trial, the average weight loss in the intensive intervention arm was $6.9\% \pm 4.5\%$ after 6 months of follow up and $4.9\% \pm 7.4\%$ at the end of the trial (mean follow-up of 3.2 years).⁵⁵ This percent weight loss is similar to other studies and greater than that observed in the SDPI evaluation where Jiang et al reported a percent weight loss of 4.4% following the 16-week program.¹⁰ Based on this literature, we expect a mean percent weight loss of 4.0% in the standard DPP and 6.5% in the enhanced DPP. To be conservative, we powered the study to be able to detect a difference of 2.0%. Dividing a 2.0% difference (6.0%-4.0%) by the DPP SD (4.5%) yields an effect size of approximately 0.45. A sample of 81 participants per arm will be required to compare the standard and enhanced arms for an effect size of 0.45 at a two-sided $\alpha=0.05$ with 80% power. We estimate 20% will be missing BMI at follow-up and have therefore inflated the initial sample size to 102 participants per arm. As the secondary analyses are exploratory, no adjustment for multiple testing will be made for secondary analyses. The secondary analyses are not intended to produce clinically actionable results, but rather to supplement conclusions based on the primary analysis and to inform future research. They will be interpreted properly within that context, considering the totality of evidence available.

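### The plan does not guarantee every cohort the visit behind the 12-month primary test, nor say whether the 20% missing-BMI allowance covers visits never scheduled

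*Protocol*

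**What the plan says.** Protocol section 2.a (Procedures) plans shorter follow-up for late entrants: "Participants enrolled in the last cohorts will not have as many follow-up evaluations as those enrolled in initial cohorts". It does not say which visits go, how many cohorts or participants are affected, or which visit everyone must reach.

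The protocol's timetable is not consistent:
- Section 2.a: "Participants will complete 3 evaluations during the research study: baseline, 5 months (1 week following the conclusion of intervention". This counts three evaluations and names two.
- Section 2.a, later in the same paragraph: "Questionnaires will be filled out at the clinic visits at baseline, 5 months, 8 months, 14 months, and 20 months". This makes five time points, none at 12 months.
- Section 4.h, exclusion x: "Plans to move during the study period (9 months post-randomization".
- Section 2.g (Study Endpoint(s)): "We plan to continue the study for the full 20 months".

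The SAP (METHODS) models months 6, 12 and 18 and places the primary test at the second: "To test whether the change in the primary outcome from baseline at 12 months differs between the standard and enhanced arms". The null hypothesis is a zero intervention-by-month-12 coefficient, tested "using the Wald test". The primary analysis uses whatever data are available. Multiple imputation and a worst-case fill appear among the sensitivity analyses.

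On size, the SAP says: "We estimate 20% will be missing BMI at follow-up and have therefore inflated the initial sample size to 102 participants per arm". Its caveat that actual power may differ names the cohort effect and the repeated measures. Shortened follow-up is not mentioned.

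**The concern.** The primary comparison rests on one late time point, and the protocol plans for some participants to have fewer visits without protecting that time point. If the protocol's 14-month visit is meant to supply the 12-month value, a cohort that loses its last two visits has no primary outcome. If three evaluations means baseline, 5 and 8 months, the same is true. The 9-month study period in the exclusion criteria makes such early truncation plausible.

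Two things are at stake. The first is precision: the evaluable number was set with almost nothing to spare. The second is the worst-case sensitivity analysis. The SAP does not separate a visit that was missed from one that was never planned, so an extreme value could be entered for people whose only feature is a late enrolment date.

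**Working it through.** **Inputs from the SAP (SAMPLE SIZE AND DATA INTERPRETATION):** difference 2.0 points of percent weight loss, SD 4.5, two-sided alpha 0.05, power 80%, 81 per arm, 20% missing, 102 per arm. **Not given in the documents:** the fraction f of participants never scheduled for the primary visit. It is shown as a range.

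**Step 1: reproduce the plan.** Effect size = 2.0/4.5 = 0.444. A two-sample t-test needs 80.44, so 81 per arm (power 80.3%). Inflation: 81/0.80 = 101.25, so 102. Both figures reproduce.

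**Step 2: the reserve.** 102 x 0.80 = 81.6, against 81.

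**Step 3: complete-case power if the 20% applies only to those scheduled.** Evaluable n per arm = 102 x 0.80 x (1 - f), t-test at 0.444:

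| f | Evaluable per arm | Total missing | Power | Difference detectable at 80% power |
|---|---|---|---|---|
| 10% | 73.4 | 28% | 76.3% | 2.09 |
| 20% | 65.3 | 36% | 71.2% | 2.22 |
| 30% | 57.1 | 44% | 65.4% | 2.38 |
| 40% | 49.0 | 52% | 58.6% | 2.57 |

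**Step 4: where power crosses 80%.** With the t-test at 0.444, f = 1 - 80.44/81.6 = 1.4%. With the normal approximation the crossing is at 2.6% (effect size 0.444) or 5.0% (rounded effect size 0.45). So the threshold is about 1% to 5%, depending on formula and rounding.

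**Step 5: allow for the mixed model.** Earlier visits of truncated participants contribute. As an approximation, with correlation r between the earlier change and the 12-month change, effective n = 81.6 / [(1 - r²)/(1 - f) + r²]. The documents give no r. At f = 20%:
- r = 0.5: 81.6/1.1875 = 68.7, power about 73.5%
- r = 0.7: 81.6/1.1275 = 72.4, power about 75.7%
- r = 0.8: 81.6/1.09 = 74.9, power about 77.1%

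**Step 6: the other reading of the 20%.** If it includes never-scheduled visits, evaluable n stays at 81.6 and power at about 80%. The room left for ordinary missingness among those scheduled is then 1 - 0.80/(1 - f): 11% at f = 10%, and none at f = 20%.

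**Step 7: recruiting more.** Keeping 81 evaluable needs 81/[0.80 x (1 - f)] randomised per arm: 113 at f = 10%, 127 at 20%, 145 at 30%. Even 113 per arm is 226 in total, above the protocol's ceiling of 210.

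**The case against.** A reader might infer that the 20% allowance leaves these participants out and that the trial is therefore underpowered. The documents do not establish this. The 20% is a single figure with no stated cause, and it may have been meant to include visits never scheduled. Nor does the protocol say that the tested visit is among those cut. If only later visits are lost, f is zero at the primary time point and nothing changes. No document gives the number, size or calendar of the cohorts, so the range for f is illustrative. The garbled count of three evaluations needs correcting, but does not show that anyone misses the tested visit.

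A reader might also infer that the SAP imputes every absent value. It does not: the primary analysis imputes nothing, and imputation is confined to sensitivity analyses. Multiple imputation under missing-at-random is reasonable when absence is fixed by entry date. Only the worst-case fill is a real difficulty.

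Finally, a reader might infer bias. Absence decided by entry date should be similar in the two arms if randomisation runs within cohorts, so the expected effect is on precision, although the 12-month estimate would lean on the earlier cohorts.

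These objections limit the claim but do not remove it. The documents still do not show who is scheduled to supply the primary outcome, and the sample size cannot absorb more than a few percent who are not.

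**Conclusion.** The point holds as a conditional one. The plan does not guarantee the primary visit to every cohort, has no protocol visit at the tested month, and does not say what its 20% covers. If the 20% is ordinary missingness among those scheduled, the stated 80% is lost at a shortfall of about 1% to 5%. The complete-case figures in the table overstate the loss under the planned mixed model, but even there power at f = 20% is about 73% to 77% for correlations of 0.5 to 0.8. If the 20% already includes never-scheduled visits, or truncation removes only visits after the primary one, about 80% stands. All figures take the SAP's own difference and SD as given. That the effect is on precision rather than bias rests on randomisation within cohorts, which the documents do not state.

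**What to change.** 1. **Protocol section 2.a and SAP METHODS.** Reconcile 5, 8, 14 and 20 months with 6, 12 and 18. Name the visit that supplies the primary outcome, and state that truncation may remove only visits after it. Align the count of three evaluations with the schedule, and reconcile it with the 9-month study period in section 4.h (repeated in 4.i) and the 20 months in section 2.g. The cost is wording, plus longer follow-up and an added visit for any cohort now cut earlier.
2. **SAP SAMPLE SIZE AND DATA INTERPRETATION, if item 1 is not possible.** State how many participants are scheduled for the primary visit, take 0.80 of that as the evaluable number, and restate the power or detectable difference. Alternatively, confirm that the 20% includes never-scheduled visits and give the ordinary missingness that this leaves room for. The cost may be a less favourable stated power.
3. **SAP METHODS, missing data.** Classify never-scheduled visits as administrative and exclude them from the worst-case fill. Multiple imputation under missing-at-random may keep them. Report missingness at the primary visit among those scheduled for it. This costs only wording.
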